If naltrexone-induced hepatitis were to occur in the setting of depot, where the naltrexone would be only very slowly eliminated, this would prolong exposure to the offending agent. However, the experience with long-acting injectable naltrexone also suggests it is safe. In our studies with long-acting naltrexone several patients experienced elevation in liver enzymes, which were determined to be related to hepatitis C. One patient in the depot naltrexone trial developed diabetes mellitus, which was deemed unlikely to be study related.

During the outpatient detoxification phase of the study, patients will have daily doses of oral naltrexone supervised at **the clinic**. If a patient misses one or more oral naltrexone doses and resumes regular opiate use, then taking a dose of naltrexone will precipitate opiate withdrawal, which may be quite severe. Patients will be warned not to take the naltrexone if they have missed their dose for more than three days in a row and resumed opiate use for more than one day. They will be told that the reaction could resemble that experienced during the initial buprenorphine-clonidine-naltrexone procedure. Patients will be advised to report to **the clinic** for clinical assessment by a study physician. If history and urine toxicology findings suggest a lapse or possible relapse, a naloxone challenge may be necessary. If the naloxone challenge is positive (withdrawal is precipitated), then the patient will be managed according to guidelines described above (see section entitled Handling of Lapses and Relapses).

Relapsed patients who cannot resume naltrexone are referred for inpatient detoxification or outpatient buprenorphine or methadone maintenance. Self-administration of large doses of opiates may override the blockade produced by naltrexone, resulting in opiate overdose with its attendant risks including respiratory depression and death. Patients will be warned of the severe danger of trying to override the blockade. Also patients who have stopped naltrexone for several days and resume opiates will not be tolerant initially, so that the quantities of opiates self administered prior to treatment, when they were tolerant, may be quite dangerous in the non-tolerant state. Patients will be warned of this. Patients with a history of drug overdose in the past 3 years will be excluded.

Patients who self-administer opiates to the point of somnolence or stupor will be removed from the trial and referred to inpatient detoxification or to methadone maintenance treatment. It is notable that XR-naltrexone in theory might protect against this risk, since naltrexone blood levels decline gradually over a period of weeks rather than the abrupt decline which occurs when oral naltrexone is discontinued. In the event of a medical emergency requiring opiate analgesia, a patient on naltrexone will require higher doses of opiates than normally administered. Patients will be informed of this and will be given a naltrexone medication card to carry in their wallet.

Pregnancy

Both the buprenorphine-clonidine-naltrexone procedure and naltrexone maintenance are considered contraindicated in pregnancy. Several small case series (Hulse et al., 2001; 2004) are reassuring in suggesting favorable pregnancy outcomes in women detoxified and maintained on naltrexone while pregnant. However, standard practice suggests methadone maintenance is the treatment of choice for opioid dependent pregnant women, and we do not consider the small size of these case series sufficient to amend that recommendation. Absence of pregnancy will be confirmed at baseline and monthly during the study with urinary HCG. During the screening period, a serum (quantitative) pregnancy test will be obtained prior to administration of XR-naltrexone. For women, regular use of an adequate contraception method (diaphragm with spermicide, condom with spermicide, birth control pills) is required for inclusion in the study. In addition, urine pregnancy will be tested on Day 5 or Day 10, prior to administration of XR-NTX. Patients who become pregnant during the trial will be removed from the trial and treated as clinically indicated.

Blood Tests

Blood drawing may cause slight discomfort at site of needle entry, resulting in a small bruise.

Naloxone Challenge Test

This test will be performed under the supervision of a study physician and will take approximately 45 min to complete. The risks of a dose of 0.2-0.8 mg naloxone administered IM are the signs and symptoms associated with opioid withdrawal (“gooseflesh,” “vomiting,” “tremor,” “uncontrollable yawning,” etc.). These will be assessed every 10 min. for up to 45 min. During the procedure, we will measure blood pressure and heart rate before and up to 30 min. after the naloxone dose.

Intramuscular Injection of Naltrexone

XR-NTX injections may be followed by pain, tenderness, induration, abscess, sterile abscess, and pruritus. Cases of serious injection site reactions, some of which involved surgical intervention, have been reported. Participants will be evaluated for injection site reaction at each outpatient visit, and will be educated about signs and symptoms of site reaction and will be encouraged to bring it to the attention of medical staff if any of these occurs. Injection with this formulation of depot naltrexone (XR-NTX) was well tolerated in over 400 alcohol-dependent patients treated with monthly injections for 6 months in the pivotal trial leading to FDA approval for alcohol dependence (Garbutt et al 2005, Anton et al. 2006). More recently, XR-NTX has been approved by FDA for the prevention of relapse to opioid dependence, following opioid detoxification.

Risks associated with receiving vouchers or cash equivalents

During outpatient treatment participants will receive vouchers or cash equivalents, which could pose a risk of using the cash to buy drugs. In response, we have developed procedures to minimize and protect against this risk. A voucher incentive system is being used to compensate patients for their time and travel and to encourage compliance with study procedures. For that purpose we have adopted procedures used widely in the context of Contingency Management Therapy. We believe that using low-value incentives is essential to maximize participation in study-related procedures, including nursing and physician visits for safety monitoring, study outcomes collection, and therapy participation. At each visit patients will earn \$15 after completing all procedures scheduled for this visit. Risks that participants will attempt to use study payments to purchase drugs, though still present, are rather small with current procedures.

Describe procedures for minimizing risks

Exclusion Criteria: The exclusion criteria of this study are designed to minimize the risks to patientparticipants. Patients are excluded if they have severe psychiatric illness (mood disorder with functional impairment or suicide risk, schizophrenia) which might interfere with their ability to participate in the outpatient therapy. A history of drug overdoses will be exclusionary. Pregnancy, lactation, or failure to practice a reliable birth control method is exclusionary, and patients are instructed to inform their psychiatrist immediately if they suspect they may be pregnant. Urine HCG is tested during screening and monthly throughout the trial. Serum (quantitative) pregnancy test will be obtained during screening. The baseline medical evaluation includes physical examination, blood chemistry profile (including liver function tests), complete blood count, urinalysis (including HCG), and electrocardiogram, urine toxicology, and naloxone challenge if opiate dependence diagnosis is unclear. The evaluating psychiatrist reviews all these and takes a medical history.

Any disorders which might make buprenorphine-clonidine-naltrexone or naltrexone maintenance hazardous, such as uncontrolled hypertension, diabetes, heart disease, hepatitis with transaminase levels greater than three times the upper limit of normal, renal disease, or advanced AIDS are exclusionary. Participants with uncertain hepatitis status and unexplained liver enzyme elevation > 5 times the upper limit of normal will be offered hepatitis panel testing to determine study eligibility. Patients with acute hepatitis infection and increasing liver function tests during screening will be excluded from study participation. The patient will

be assisted in obtaining appropriate medical evaluation and treatment, and may be eligible for the research study once the problem is controlled. History of an allergic reaction to any of the medications used is an exclusion criterion.

Patient Education: All patients will be informed through the informed consent form and discussions with the research psychiatrist and therapist of the possible side effects and risks enumerated above. In addition, at monthly visits the psychiatrist will query side effects in general, and events of specific concern including missing naltrexone doses in conjunction with resumed opiate use or heavy opiate use in an effort to override the blockade, and the risk of overdose and death in these situations. Therapists will also be trained to query for such events and bring them to the attention of the psychiatrist who will follow up. Patients will give informed consent before entering the study. Patients are instructed to call us if any untoward effects occur and are given the phone number of our 24-hour answering service.

Patient Monitoring and Removal from Study: The psychiatrist and/or therapist will assess appropriateness for continuation in the research study on a continuous basis, and will remove from the trial patients with significant clinical deterioration or noncompliance of a type which could be dangerous. Criteria for removal from the study will include:

- 1.) Relapse to opiate dependence: This will be suspected if a patient misses more than three days in a row of naltrexone and resumes opiate use for more than three days during that time and produces an opiate positive urine. It may be confirmed with a naloxone challenge.
- 2.) Binges of opiate use with the intent to over-ride the blockade produced by naltrexone, or opiate use resulting in severe intoxication or somnolence.
- 3.) Seven (7) consecutive missed days during detoxification period or 14 consecutive missed days post-XR-NTX induction (unless they are in contact with clinic staff).
- 4.) Other clinical deterioration which cannot be managed safely in the context of outpatient treatment. This would include a patient who becomes suicidal, or a patient who goes on severe drug binges (including nonopiate drugs), endangering him/herself, or CGI-S>6.
- 5.) Elevation of liver enzymes In the injectable naltrexone condition, if liver enzyme are elevated > 3 times normal, the next injection will be delayed.

A hepatitis panel will be obtained and liver enzymes repeated; long-acting injectable naltrexone will not be re-administered until liver enzymes fall below 3 times upper limit of normal. If liver enzymes do not improve, the subject will discontinue naltrexone.

If a patient is removed from the research trial for medical reasons, he/she will be retained in open treatment for the remaining of the study period and will be offered a supply of buprenorphine while transitioning to other treatment. Upon removal of a patient from the trial due to clinical deterioration, the patient will be referred for appropriate follow-up treatment, in most instances either inpatient detoxification or residential treatment, or methadone maintenance. The PI, Co-PI, or a study psychiatrist is available 24 hours/day by phone and/or beeper in case of emergency.

Methods to Protect Confidentiality

Describe methods to protect confidentiality

Confidentiality: In the course of treatment, patients may divulge information which is sensitive and may have adverse social consequences if released. This would include information released to insurance companies, family members, or made public in any way. Patient records are kept in locked files and released only with the patient's consent. Contact with family members or significant others is made only with the patient's express consent. Audiotaped psychotherapy sessions and digital CD-ROMS created from these sessions will be stored in locked cabinets without any identifying information, and destroyed after 10 years. All mainframe computer and microcomputer data is stored without names or other uncoded identification. Patients will be identified only through a numerical code in both the mainframe and microcomputer databases, while a paper code list will be kept under lock and key by the PI and the Research Assistant. A Federal Certificate of Confidentiality will be obtained.

Will the study be conducted under a certificate of confidentiality?

Yes, we will apply for the Certificate of Confidentiality

Direct Benefits to Subjects

Direct Benefits to Subjects

Participants may benefit from many of the components of the treatment that they receive, induction onto injection naltrexone, naltrexone maintenance, and components of behavioral therapy.

Compensation and/or Reimbursement

Will compensation or reimbursement for expenses be offered to subjects?

Yes

Please describe and indicate total amount and schedule of payment(s).

Include justification for compensation amounts and indicate if there are bonus payments.

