Primary Hypothesis 1: Adjunctive treatment with buprenorphine 4 mg during the first 5 weeks of naltrexone maintenance will improve opioid abstinence and treatment retention, defined as receiving the second XR-NTX injection.

Primary Hypothesis 2: Providing buprenorphine 4 mg daily during gradual 9-day titration of oral naltrexone will improve tolerability and success of XR-NTX induction, defined as receiving the first XR-NTX injection.

Primary Hypothesis 3: Providing buprenorphine 4 mg daily during gradual 9-day titration of oral naltrexone and adjunctive treatment with buprenorphine 4 mg during the first 5 weeks of naltrexone maintenance will significantly improve opioid abstinence and treatment retention, defined as receiving the second XR-NTX injection.

Primary Aim 4: To examine in biofluid-derived extracellular vesicle content for the existence of biomarkers related to naltrexone treatment.

Description of Subject Population

Sample #1

Specify subject population

Adults with current Opioid Use Disorder

Number of completers required to accomplish study aims

15

Projected number of subjects who will be enrolled to obtain required number of completers

30

Age range of subject population

18-60

Gender, Racial and Ethnic Breakdown

Both genders and all ethnic groups are eligible. It is estimated that the sample will be 60% male, 40% female, 50% Caucasian, 30% Hispanic-American, 15% African-American, and 5% other minorities based on data from previous trials.

Description of subject population

Prospective participants must be adult (18 to 60 years of age) and meet criteria for current opioid use disorder by history and urine toxicology. Other substance use diagnoses are not exclusionary since multiple substance abuse is common in this population, and such an exclusion would rule out a large proportion of the population and limit the generalizability of the study. However, physiological dependence on alcohol or sedative-hypnotics with impending withdrawal is exclusionary. Maintenance on methadone or other long-acting agonist (e.g. buprenorphine) or regular use of illicit methadone (> 30 mg per week) is exclusionary. Prospective participants cannot have concurrent psychiatric or medical conditions that would interfere with

participation (e.g. mania, psychosis, suicidality, pregnancy or failure to use adequate contraception).

Recruitment Procedures

Describe settings where recruitment will occur

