Patients will undergo an outpatient buprenorphine-clonidine-naltrexone procedure to initiate treatment with XR-naltrexone (XR-NTX) as developed at STARS (Sullivan et al., in print). At the end of the procedure, after the injection of XR-NTX participants will begin treatment with buprenorphine 4 mg/d for 4 weeks, after which they will receive another injection of XR-NTX and will continue with buprenorphine for additional 4 days up to the total of 5 weeks of buprenorphine.

Rationale

Adding buprenorphine after the transition onto XR-naltrexone will not produce any significant opioid agonist effect (as it will be blocked by naltrexone) but will add an additional kappa antagonist effect which may help alleviate residual/protracted withdrawal symptoms. This is a replication study of the method previously published by Gerra et al. (2006) with oral naltrexone.

Study Medications Dosing

On the morning of Day 1, participants will receive 2 mg of buprenorphine, to be followed by a second dose after 1-2 hours. Participants will receive a total of 8mg of buprenorphine on Day 1. One washout day follows which includes administration of adjuvant medications. On Day 3, after pre-treatment with prochlorperazine 10mg for nausea, the first dose of naltrexone 1 mg is given, followed by ascending doses titrated gradually, as tolerated, to 25 mg on Day 5. Adherence will be supported by observed ingestion of powdered doses of naltrexone as suspension in water. Participants will receive XR-NTX on Day 5 together with buprenorphine 4mg, and will continue to receive BUP 4 mg/d for 4 weeks until they receive the 2nd XR-NTX dose. Participants will receive the total of two doses of XR-NTX.

Participants will receive 8mg buprenorphine on Day 1 of the detoxification, and following administration of XR-NTX will receive 4mg buprenorphine daily for four weeks of outpatient treatment. All participants will be receiving a sublingual tablet once daily. Buprenorphine will be discontinued the day after the 2nd injection of XR-NTX. Buprenorphine will be given once daily, starting after administration of 25mg of naltrexone. The dose of 4 mg will be continued at the 4mg until administration of 2nd XR-NTX dose. Following the second XR-NTX injection buprenorphine dose will be decreased to 2 mg for 4 days after which it will be stopped.

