Procedure 3 is a combination of procedure 1 (BUP 4 mg/d given in combination with XR-NTX) and procedure 2 (slow titration of oral naltrexone while maintaining stable BUP dose).

Rationale

This is a combination of Procedure 1 and 3

Study Medications Dosing

On the morning of Day 1, participants will receive 2 mg of buprenorphine, to be followed by a second dose after 1-2 hours. Participants will receive a total of 8mg of buprenorphine on Day 1. Patients will then receive 4mg of buprenorphine on Days 2-10. Beginning on Day 2 participants will receive increasing doses of naltrexone 30 minutes after the dose of buprenorphine 4mg has been administered, starting with 0.25mg titrating up to 25mg on Day 10 (Day 2:0.25mg; Day 3: 0.5mg; Day 4: 1mg; Day 5: 2mg; Day 6: 3mg; Day 7: 6mg; Day 8: 12mg; Day 9: 25mg; Day 10: 25mg. Participants will receive XR-NTX on Day 10 together with buprenorphine 4mg, and will continue to receive buprenorphine 4mg for 4 weeks until they receive the 2nd XR-NTX dose. Following the second XR-NTX injection, the buprenorphine dose will be decreased in Study Week 5 to 2 mg for 4 days after which it will be stopped.

If a significant withdrawal symptoms emerge during the naltrexone titration, the next dose of naltrexone will be repeated (rather than doubled) and therefore the procedure may be slowed by 1-3 days. Once a patient has tolerated a first daily dose of naltrexone 25 mg, he/she is eligible to receive XR-NTX 380 mg IM.

Adjuvant medications (Procedures 2 & 3)

We believe that there will be less withdrawal symptoms in participants receiving buprenorphine therefore we will use lower standing doses of medications with the option to administer additional doses as needed for breakthrough withdrawal. We will administer Clonidine 0.1 mg BID and clonazepam 0.5 mg BID daily. Additional doses of clonidine 0.1 mg (MDD=0.4 mg), clonazepam 0.5 mg (MDD=2.0 mg), prochlorperazine 10 mg QD, trazodone 100 mg HS, and zolpidem 10 mg HS will be administered as needed. Clonidine will be held if blood pressure falls below 90/60 mm Hg at any visit's vitals check. Adjuvant medications will be offered for one week following administration of XR-NTX as needed for persistent withdrawal symptoms.

Treatment Period

Adherence to oral naltrexone

All doses of buprenorphine and oral naltrexone will be directly observed when possible. If a significant withdrawal symptoms emerge during the naltrexone titration, the next dose of naltrexone will be repeated

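### Procedure 1's dosing text gives two incompatible rules for ending buprenorphine after the second XR-NTX injection, and Hypotheses 1 and 3 name a week-5 dose that the dosing text does not

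*Protocol*

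**What the plan says.** Protocol, Procedure 1, Study Medications Dosing, contains three sentences on how buprenorphine ends:

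- One stops the drug outright: "Buprenorphine will be discontinued the day after the 2nd injection of XR-NTX".
- Another sets how long the full dose lasts: "The dose of 4 mg will be continued at the 4mg until administration of 2nd XR-NTX dose".
- A third adds a step-down period: "Following the second XR-NTX injection buprenorphine dose will be decreased to 2 mg for 4 days after which it will be stopped".

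The Procedure 1 Design text says that after the second injection participants "will continue with buprenorphine for additional 4 days up to the total of 5 weeks of buprenorphine". It names no dose for those extra days.

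Procedure 3 (Study Medications Dosing) has a single end rule. Participants "will continue to receive buprenorphine 4mg for 4 weeks until they receive the 2nd XR-NTX dose", and after that injection "the buprenorphine dose will be decreased in Study Week 5 to 2 mg for 4 days after which it will be stopped".

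The hypotheses (Protocol, Specific Aims and Hypotheses) describe the regimen differently. Hypothesis 1: "Adjunctive treatment with buprenorphine 4 mg during the first 5 weeks of naltrexone maintenance will improve opioid abstinence and treatment retention". Hypothesis 3: "adjunctive treatment with buprenorphine 4 mg during the first 5 weeks of naltrexone maintenance will significantly improve opioid abstinence and treatment retention". The SAP, Study Hypotheses, repeats the same dose and duration for Procedures 1 and 3.

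**The concern.** A participant cannot be off buprenorphine from the day after the second injection and also take 2 mg for four days after it. Neither sentence is marked as superseded, and nothing elsewhere in the protocol or SAP says which governs.

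The practical moment is the second-injection visit. The protocol's section on the risks of the induction procedure says that buprenorphine is dispensed weekly once the first injection has been given. At that visit staff must decide what supply, if any, goes home for the next week, and the dosing text supports two answers. Participants in a group of 10 could then be treated differently. The withdrawal, adverse-event and opioid-use data from those days, which feed the SAP's residual-withdrawal measure and adverse-event summary, would come from an unclear regimen.

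The hypotheses add a reporting problem. A pilot should be able to state the regimen it tested, and for week 5 the hypotheses and the dosing text name different doses.

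**Working it through.** **Calendar.** Injection 1 is day 0, with the first 4 mg dose that day (Procedure 1, Study Medications Dosing). Injection 2 is day 28, four weeks later, if on schedule. The 8 mg given on induction Day 1 is common to both rules and is left out unless stated.

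**The plan's own figure.** The Design text speaks of up to 5 weeks in total. Four weeks plus 4 days is 28 + 4 = 32 days, or 33 if the injection-2 day is a further 4 mg day. That is 32/7 = 4.57 to 33/7 = 4.71 weeks. Adding induction Day 1 gives 33 to 34 days, 4.71 to 4.86 weeks. So 5 weeks is a fair rounding of duration, provided dosing continues for 4 days after injection 2.

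**The two end rules.** Rule A is the stop on the day after injection 2. Rule B is 2 mg for 4 days. Each can be read two ways:

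| Reading | Doses | Last dose | Total |
|---|---|---|---|
| A1: no dose on day 29 | 29 × 4 mg | day 28 | 116 mg |
| A2: last dose on day 29 | 30 × 4 mg | day 29 | 120 mg |
| B1: 4 mg on day 28, 2 mg on days 29–32 | 29 × 4 + 4 × 2 mg | day 32 | 124 mg |
| B2: 2 mg on days 28–31 | 28 × 4 + 4 × 2 mg | day 31 | 120 mg |

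Differences, B minus A:

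- B1 − A1: 4 days, 8 mg
- B1 − A2: 3 days, 4 mg
- B2 − A1: 3 days, 4 mg
- B2 − A2: 2 days, 0 mg

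The full range is therefore 2 to 4 days and 0 to 8 mg. Reading A2 gives 4 mg on the day after injection 2, which sits badly with the sentence holding 4 mg only until that injection. Without A2 the range is 3 to 4 days and 4 to 8 mg. Leaving the day-0 dose out of the count lowers all four totals by 4 mg and changes no difference.

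**Share of follow-up.** The final study day is 28 days after injection 2, so at most 4 of 28 days are in dispute. Twice-weekly visits in weeks 5–8 make 4 × 2 = 8. If one of these is the day-28 visit, days 29–32 hold 0 or 1 further visit.

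**Primary percentages.** The SAP (Study Outcome Measures, Study Analysis) counts receipt of both injections for Procedures 1 and 3, and of the first injection for Procedure 2. Both end rules take effect only once injection 2 has been given, so they apply only to participants who have already met the endpoint.

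**Hypotheses against dosing text.** Read literally, 4 mg for 5 weeks is 5 × 7 = 35 days. On schedule, the readings above give 28 (B2), 29 (A1, B1) or 30 (A2) days at 4 mg. The shortfall is 35 − 30 = 5 to 35 − 28 = 7 days. Procedure 3, with its one end rule, gives 28 or 29 days at 4 mg from injection 1. These are on-schedule figures: if injection 2 came 7 days late, on day 35, and 4 mg ran until then, the 4 mg dose would last 35 or 36 days.

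**The case against.** The strongest case for leaving the text alone has three parts.

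- **The effect is very small.** It is a few milligrams over a few days, in a fraction of 10 participants, in a descriptive study with no comparison planned for that period. This stands, and it is why the point is minor.
- **The first sentence could mean only that the 4 mg dose ends.** The words do not support this. Their subject is buprenorphine, without a dose, and a separate sentence ends the 4 mg dose at injection 2, not the day after.
- **The other texts could guide staff.** The Procedure 1 Design text and Procedure 3 both describe dosing after injection 2. But the Design text names no dose and Procedure 3 is a different procedure. Neither cancels a current dosing instruction.

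On the hypotheses, the objection that 5 weeks is shorthand largely succeeds. It matches the 5-week total in the Design text and the Study Week 5 step in Procedure 3. Only the dose named for week 5 remains inconsistent.

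Two stronger readings are tempting and should not be adopted. A reader might infer that a fifth week of buprenorphine cannot bear on retention, because the second injection is due at 4 weeks. But the protocol's section on missed XR-NTX doses allows a late injection within a grace period of at least 7 days, and the SAP (Study Participants and Design) says approximately 4 weeks. A second injection can therefore fall in week 5. The hypotheses also name opioid abstinence, which week 5 can affect.

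A reader might also infer that the affected records begin at injection 2. They do not: withdrawal scales run from induction, and visits run twice weekly from week 1 (Assessment Instruments, Study Visits). Only the End-of-Study Form's abstinence status, covering the last four weeks, opens near injection 2 for completers.

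**Conclusion.** The contradiction in Procedure 1 is real and nothing else in the documents resolves it. It is a minor conduct and reporting defect. With injection 2 at day 28, it amounts to about 2 to 4 days and 0 to 8 mg per participant, for those of the 10 planned Procedure 1 participants who receive that injection. The exact figures depend on end-day conventions that the text leaves open.

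A reader might infer that the primary result is at risk. It is not, because both rules act only after the endpoint has been met. What is affected is uniform dispensing at the second-injection visit and the interpretation of a few days of withdrawal, adverse-event and abstinence data.

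The hypothesis wording is a secondary note. It concerns Procedures 1 and 3, 20 of the 30 planned participants. Duration roughly agrees with the dosing text where dosing continues after injection 2; the dose named for week 5 does not.

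**What to change.** Reconcile the conflicting sentences in Procedure 1, Study Medications Dosing, together with the Procedure 1 Design text, so that Procedure 1 has one rule for the dose, timing and end of buprenorphine after the second injection. Then word Hypotheses 1 and 3, in the protocol and in the SAP's Study Hypotheses, so that they name the same regimen as the Procedure 1 and Procedure 3 dosing text. Which passage is right is for the investigators to decide.

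The cost is wording in two documents, with no added participants, visits or analyses.
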